- 2.2. Describe how randomization or other treatment assignment will be made. **Veterans who meet criteria for participation will be randomly assigned to one of the two treatment conditions. Urn randomization will be used to balance the groups on three factors: gender, benzodiazepine or other drug use, and age. We will also be blocking on whether the person admits use or not when we do the randomization, so we get equal numbers of non-users in each condition. Urn randomization is a kind of biased-coin randomization where probability of being assigned to a group decreases if the group is overrepresented and increases if the group is underrepresented. As the sample size increases, the randomization shifts from perfect balance to complete randomization.**
- 2.3. For retrospective research studies, provide the "look-back" period. (e.g., December 1, 1999 through December 31, 2008.) **n/a**

3. **Study Duration**

- 3.1. Provide the estimated length of time to enroll all subjects and complete the study. **2.5 years of enrollment, but 5 years total for study start up, enrollment, completion, and analyses.**
- 3.2. Explain the expected duration of subject participation including any follow-up. **18 months for patients enrolled prior to 4/1/2019; 12 months for patients enrolled after 4/1/2019**
- 3.3. Specify the projected date of completion of the proposed study. **5 years from date of funding.**

4. **Drug Information** (If not applicable state, "Not Applicable.") **Not Applicable**

- 4.1. Specify if the drug or biological agent is:
  - 4.1.1. FDA approved
  - 4.1.2. Used for off-label purposes
  - 4.1.3. Not yet FDA approved.
- 4.2. Include the FDA Investigational New Drug (IND) number for all non-FDA approved and off-label drugs, biological agents or nutritional supplements. If not applicable state, "Not Applicable."
- 4.3. Provide all relevant information about the drug
- 4.4. Explain any wash-out periods, rescue medications permitted and any type of medications not permitted while enrolled in the study.
- 4.5. Describe blinding and un-blinding procedures.

- 4.6. Include the dosage, route of administration, previous use, and the safety and efficacy information on any drug used for research purposes.
- 4.7. Describe rationale for the dosage in this study.
- 4.8. Justify why the risks are reasonable in relation to anticipated benefits and/or knowledge.
- 4.9. Describe where drug preparation will be done.

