- If they are not eligible for the study and the Participant will not be contacted again. No referral or communication of results will be made. If they are ineligible due to screening positive for a substance use disorder (by having 5 or more symptoms on the exclusion checklist), then they are drinking (or using) at too high a level and the results of this screening will be communicated to BHL for further clinical care.
- If they are not currently receiving mental health services at the MHC, and eligible: If Veteran decides to participate, a study counselor will complete the Brief Intervention only after participant has been consented to participate in the study and admits to any drinking. If the counselor determines their alcohol use is severe enough to necessitate more intensive treatment (i.e. inpatient treatment), the Veteran will be referred to the higher level of care and will be removed from our study. If Veteran decides not to participate, the technician will thank them for their time and end the call. A research note describing the outcome of screening call will be created in CPRS.
- If they are currently receiving mental health services at the MHC, and eligible: If Veteran decides to participate, a study counselor will complete the Brief Intervention only after participant has been consented to participate in the study. If Veteran decides not to participate or is later found to be ineligible, standard care through the MHC will continue as if he/she had never been contacted about the study. A research note describing the outcome of screening call will be created in CPRS.
- If they are not currently receiving mental health services at the MHC, and ineligible: A research note describing the outcome of screening call will be created in CPRS.
- If they are currently receiving mental health services at the MHC, and ineligible: Standard care will continue through the MHC as if the Veteran had never been referred to the study. A research note describing the outcome of screening call will be created in CPRS.

- It is possible through the course of receiving care at the CMCVAMC that a Veteran has received a BI in the past. However, this treatment could have occurred far enough in the past (i.e. greater than 3 months) that the BI would need to be repeated. As we cannot ensure a Veteran has received a recent (within the past 3 months) BI through the MHC, the study staff will perform the BI's for those Veterans.

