For those who are potentially eligible following the phone screen (and interested in participating), the next step is coming to the VA for consent. After consent, subjects will complete the first research visit. Final eligibility is determined after consent using the SCID and MINI. If after learning more about the study during the consenting process, the Veteran decides not to consent, or if they are ineligible following the SCID and MINI, then the Veteran will continue to receive services at the CMCVAMC to which they are eligible and entitled to. This could include services through the BHL or MHC. Similarly, Veterans can also elect to stop their participation in the study and can withdraw without penalty in writing using the revocation form at any time after they have consented to the study. In this case, their normal care at the CMCVAMC will continue.

Veterans who meet criteria for participation will be randomly assigned to either receive the usual care (that which they would have gotten if they had not chosen to be in the study); or Prevention Intervention (PI).

As a result of relaxing our inclusion criteria, it is likely that we will randomize Veterans who have not consumed alcohol in the past three months. For those Veterans, we will monitor their alcohol use during the research follow up visits at 3, 6, and 9 months. If they report having a drink of alcohol, we will then begin which treatment arm they had been randomized to. If the Veteran does not report taking a drink prior to the 9 month follow up, they will simply continue with the 12 and 18 month follow ups but will never have the Brief Intervention or Prevention Intervention.

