#### Brief Intervention (BI)

Both groups will have received or will be scheduled to receive Brief Intervention (BI). A brief intervention includes providing feedback linking the Veteran's drinking to their health issues, in addition to providing education and advice about recommended drinking limits, and how to reduce alcohol use. In general, a BI involves increasing an individual's insight about the risk of drinking on opiates, and how to cut down. However, each Veteran presents with a different situation, and thus the BI can be flexible in terms of content. Sometimes the BHL will send the NIAAA workbook "rethinking drinking" to a Veteran, sometimes they won't. Sometimes a Veteran will get a follow up call, and sometimes they won't. It depends on what the Veteran needs. So in terms of what exactly the research staff will do during BI's, it will follow a similar structure to the BHL BI's (raise insight, identify strategies on how to reduce) but the details on how to accomplish those goals will vary based on each Veteran's individual situation.

For Veterans not enrolled in the Mental Health Clinic (MHC), study staff will administer the BI since as a result of broadening our inclusion criteria these are individuals that would likely not be serviced by BHL. If during the baseline visit study staff determine that the Veteran's drinking warrants a referral to the Behavioral Health Lab (BHL) then the BHL will administer the BI. For Veterans

enrolled in the MHC, the study team will administer the BI. Study staff have worked with the BHL nurses and have all of their material and can perform BI according to standards set in the BHL protocol. Study staff will get ongoing supervision from the BHL staff, to make sure that we are following their protocol. The research counselors are Masters level clinicians trained in recovery counseling and the administration of Brief Interventions. On average, BI's take about 20 minutes, and will be done over the phone. Subjects will not be compensated for the BI done for study purposes. While not all BI's require a follow up call, following the same procedures done by the BHL, the research staff providing the BI at times will complete one or two follow up calls one month after the initial BI, to check in on an individual's progress.

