The reason why study staff needs to provide BI to subjects recruited from MHC is that BHL provides services to primary care patients. Patients already using mental health specialty care are not typically referred back to BHL for interventions like BI.

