#### R. Subject Recruitment (characteristics of the study population)

1. Provide the planned or targeted enrollment at:
  - 1.1. CMCVAMC - 115 (90 undergoing treatment and 25 just being followed and not undergoing one of the treatment groups)
  - 1.2. Other sites - 60 (10 at VA Pittsburgh; 50 at Penn)
  - 1.3. Not applicable; chart review or use of previously collected data -

2. **Screening and/or Eligibility Requirements - Inclusion/exclusion criteria are the same for screening before and after consent, however, some assessments used to determine final eligibility (such as the SCID and the MINI) are only administered once the Veteran comes to the lab (which occurs after a positive phone screen)**

2.1. Describe and provide justification for:

2.1.1. Inclusion criteria: **To be eligible for participation, Veterans must: (1) currently be receiving daily treatment with a prescription opioid for chronic pain, OR receive a daily prescription for opiate replacement therapy and have a chronic pain diagnosis; (2) be between the ages of 18 and 75; (3) have a cell phone capable of receiving text messages; (4) and be willing to be in a study where they might receive text messages.**

**If at some point during follow-up research visit, if a subject admits to drinking they will move on to the treatment arm that they were randomized to upon entry into the study.**

2.1.2. Exclusion criteria: **Veterans will not be eligible if they: (1) meet DSM-V criteria for a moderate to severe alcohol or drug disorder (with the exception of nicotine abuse/dependence); (2) have a current psychotic disorder severe enough to require inpatient treatment; or (3) are participating in alcohol use treatment at the VA or elsewhere (with exception of screening and brief intervention at the VA); (4) are currently on palliative care or are being treated with opioids for cancer-related pain.**

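### Sections O.1 and R.2.1.1 disagree on whether a baseline non-drinker who first reports drinking at month 12 starts the assigned arm, and no consistent rule gives a late reporter a brief intervention

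*Combined protocol and SAP*

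**What the plan says.** Two current sections govern when a baseline non-drinker begins treatment.

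- **Section O.1, under Referrals from BHL.** Alcohol use is monitored at the 3, 6 and 9 month research visits, and a reported drink starts the randomised arm. The alternative begins "If the Veteran does not report taking a drink prior to the 9 month follow up" and ends "they will simply continue with the 12 and 18 month follow ups but will never have the Brief Intervention or Prevention Intervention".
- **Section R.2.1.1, after the inclusion criteria.** "If at some point during follow-up research visit, if a subject admits to drinking they will move on to the treatment arm" to which they were randomised. No last visit is named.

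Follow-up visits include months 12 and 18, and the Time Line Follow-Back is taken at each (section O.1, Study visits). Section M.3.2 sets participation at "18 months for patients enrolled prior to 4/1/2019; 12 months for patients enrolled after 4/1/2019". The BI is part of both arms, takes about 20 minutes on average and is given by phone (section O.1, Brief Intervention).

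**The concern.** Staff who hear a first report of drinking at month 12 have two instructions: give nothing, or start the assigned arm. Different counselors or sites could act differently.

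There is also a care question. Section H.3 says that alcohol is implicated in opioid-related deaths more often than any other substance. The Time Line Follow-Back will show drinking at months 12 and 18, yet the O.1 rule leaves the Veteran without a BI. Usual services may not supply one. Of Veterans outside the Mental Health Clinic (MHC), the Brief Intervention section says "as a result of broadening our inclusion criteria these are individuals that would likely not be serviced by BHL". Of those inside it, "Patients already using mental health specialty care are not typically referred back to BHL for interventions like BI".

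**Working it through.** **1. The two rules side by side.** Participation left is the end of participation (month 18 or month 12, section M.3.2) minus the month of first report. The Prevention Intervention (PI) lasts 12 months (section J).

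| First report at | Section O.1 | Section R.2.1.1 | Months left, enrolled before 4/1/2019 | Months left, enrolled after |
|---|---|---|---|---|
| Month 9 | Arm starts under the monitoring sentence; the cut-off clause, read literally, excludes it | Arm starts | 18 − 9 = 9 | 12 − 9 = 3 |
| Month 12 | No arm, no BI | Arm starts | 18 − 12 = 6 | 12 − 12 = 0 |
| Month 18 | No arm, no BI | Arm starts in name only | 18 − 18 = 0 | No visit |

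At months 3 and 6 the sections agree. The conflict over starting an arm has practical effect only at month 12 in the earlier cohort, where at most 6 of PI's 12 months and one outcome window (months 13–18, section W.1) remain. The missing BI under O.1 applies to late reporters in both cohorts.

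**2. Other routes to a BI after a late first report.**

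- Section O.1, Brief Intervention: referral to the Behavioral Health Lab (BHL), tied to the baseline visit.
- Section O.1, PI overview: specialty referral, only at moderate to severe disorder.
- Section R.10.5.6.4: the clinical liaison may refer to a higher level of care.
- Section W.3.3: a consult on a significant change in use, which is not defined.
- Section H.4: annual AUDIT-C screening, averaging 86% of patients, with BHL referral at a score of 5 or more. The same section says that not all positive screens are referred.

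None sets a BI for a first report at month 12 or 18.

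**3. Size.** Section R.1 plans 25 followed-only participants among 115 at CMCVAMC: 25/115 = 21.7%. The March 2018 amendment note, used here only as context, plans 50 among 200: 50/200 = 25%. These are different enrolment plans and should not be mixed in one ratio. Neither gives a late-report rate, so 5% to 20% is assumed:

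- CMCVAMC: 25 × 0.05 = 1.25 to 25 × 0.20 = 5 people.
- Amendment plan: 50 × 0.05 = 2.5 to 50 × 0.20 = 10 people.

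An upper bound on the share of outcome data takes the larger count and gives every late reporter one affected window. With 5 or 4 windows per participant:

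- CMCVAMC: 5/(115 × 5) = 0.9%; 5/(115 × 4) = 1.1%.
- Amendment plan: 10/(200 × 5) = 1.0%; 10/(200 × 4) = 1.25%.

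The true share is smaller, since only month-12 reports in the earlier cohort have a later window. The split of enrolment at 4/1/2019 is not given.

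No power or sample size figure bears on this point.

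**The case against.** The strongest reply is that O.1 is the operating procedure and the more specific text, while R.2.1.1 is one general sentence attached to the eligibility list. An ordinary reading lets O.1 govern. That is fair, but nothing says so, and both sections are current.

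A second reply is that stopping arm starts after month 9 is sensible when PI lasts 12 months and participation ends at 18 or 12. This stands, and the fix keeps it. The month-9 ambiguity is also slight: the monitoring sentence names that visit, so the edit there is tidying.

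A third reply is that usual care, which section U.3.1 describes as including a BI, will catch late reporters. This stands in part. Annual screening and the escalation routes are a partial net, so a reader should not infer that these Veterans have no protection at all. Lower screening scores and incomplete referral leave a gap.

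A reader might also infer that O.1 already promises a BI whenever drinking is admitted, because "a study counselor will complete the Brief Intervention only after participant has been consented to participate in the study and admits to any drinking". The documents do not support that. The sentence describes one outcome of the screening call, for eligible Veterans not receiving MHC services, and it sets conditions that must precede the BI. It makes no commitment for drinking first admitted a year later.

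Finally, routine referral to clinical care could discourage honest answers. The October 2015 and March 2018 amendment notes record worry about effects on clinical care and fear of losing opioid prescriptions, and the primary outcome is self-reported. This objection stands and shapes the fix.

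**Conclusion.** The point holds as a small improvement in safety and conduct. O.1 and R.2.1.1 give opposite instructions for a first report at month 12, with practical effect only for those enrolled before 4/1/2019. Apart from the R.2.1.1 sentence that O.1 contradicts, no section provides a BI for a first report at month 12 or 18.

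The size is about 2.5 to 10 people under the amendment plan, or 1.25 to 5 at CMCVAMC, resting wholly on the assumed 5% to 20% rate. The number in the month-12 conflict is a subset that the documents do not allow one to estimate.

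A reader might infer that the treatment comparison is compromised. It is not: at most about 1% of participant-windows are involved under these assumptions, and the primary analysis and conclusions do not change.

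**What to change.** - **Section R.2.1.1:** limit the trigger to a report *at the 3, 6 or 9 month research visit*.
- **Section O.1, cut-off clause:** change the timing to *at or before the 9 month follow-up*.
- **Section O.1, consequence:** replace the statement that neither intervention will ever be given with: *will not start the assigned arm; if drinking is first reported at month 12 or 18, a study counselor will offer the phone BI in either arm, with referral to BHL or the treating clinic only if the Veteran agrees.*

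The counselor comes first because the protocol itself doubts that BHL would serve these Veterans, and because referral by consent protects candid reporting. The BI is the whole content of the comparison arm and the shared first step of PI, so offering it to late reporters in both arms adds no between-arm difference.

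The cost is a protocol amendment with IRB approval (section W.2.1.3) and about 20 counselor minutes per late reporter: 2.5 × 20 = 50 to 10 × 20 = 200 minutes over the study under the assumed rate. A few participants would receive a BI before the months 13–18 window, on the same terms in both arms. Visits, sample size and analysis stay as they are.

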#### Brief Intervention (BI)

Both groups will have received or will be scheduled to receive Brief Intervention (BI). A brief intervention includes providing feedback linking the Veteran's drinking to their health issues, in addition to providing education and advice about recommended drinking limits, and how to reduce alcohol use. In general, a BI involves increasing an individual's insight about the risk of drinking on opiates, and how to cut down. However, each Veteran presents with a different situation, and thus the BI can be flexible in terms of content. Sometimes the BHL will send the NIAAA workbook "rethinking drinking" to a Veteran, sometimes they won't. Sometimes a Veteran will get a follow up call, and sometimes they won't. It depends on what the Veteran needs. So in terms of what exactly the research staff will do during BI's, it will follow a similar structure to the BHL BI's (raise insight, identify strategies on how to reduce) but the details on how to accomplish those goals will vary based on each Veteran's individual situation.

For Veterans not enrolled in the Mental Health Clinic (MHC), study staff will administer the BI since as a result of broadening our inclusion criteria these are individuals that would likely not be serviced by BHL. If during the baseline visit study staff determine that the Veteran's drinking warrants a referral to the Behavioral Health Lab (BHL) then the BHL will administer the BI. For Veterans

enrolled in the MHC, the study team will administer the BI. Study staff have worked with the BHL nurses and have all of their material and can perform BI according to standards set in the BHL protocol. Study staff will get ongoing supervision from the BHL staff, to make sure that we are following their protocol. The research counselors are Masters level clinicians trained in recovery counseling and the administration of Brief Interventions. On average, BI's take about 20 minutes, and will be done over the phone. Subjects will not be compensated for the BI done for study purposes. While not all BI's require a follow up call, following the same procedures done by the BHL, the research staff providing the BI at times will complete one or two follow up calls one month after the initial BI, to check in on an individual's progress.

The reason why study staff needs to provide BI to subjects recruited from MHC is that BHL provides services to primary care patients. Patients already using mental health specialty care are not typically referred back to BHL for interventions like BI.

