10.5.6.1. Principal Investigator, **Monitor data and patient safety, ensure adequate training of personnel, review SAEs.**

10.5.6.2. Co-Principal Investigator, **train research counselors on integrating intervention notes into CPRS and communicate with providers in the system, review SAEs in the absence of the PI, provide clinical assistance if a participant starts to decompensate in a research visit or if a patient reveals they are a threat to themselves or others. Co-investigator will also help obtain consent.**

10.5.6.3. Research Coordinator, **ensure appropriate procedures are being followed for recruitment and consenting process, keep regulatory binder up to date; monitor accuracy of data collected and communicate with PI if there are any problems, communicate with IRB, recruitment, consenting, send informed consents and HIPAA authorizations to HIMS for scanning of documents, complete research visits.**

10.5.6.4. Additional research staff by title, **Research Technicians – recruit, consent, send informed consents and HIPAA authorizations to HIMS for scanning of documents, perform research visits, schedule follow ups.**

**Research Counselors – Recruit, consent, complete initial research visits (baseline), provide assessment, brief interventions, telephone monitoring and counseling phone calls, and monitor text messages.**

**The clinical liaison will be monitoring the phone calls made by the research counselors to ensure adherence to the manual. Additionally, the clinical liaison will be able to obtain consent in the event the two research technicians are unavailable. The clinical liaison will also have the authority to refer participants to the ARU (alcohol response unit) for a higher level of care, if needed.**

**Our research counselors are Masters level clinicians trained in recovery counseling and the administration of Brief Interventions. Our counselors received their training on how to administer a BI from clinicians within the BHL.**

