The primary outcome measure will be rates of risky drinking (i.e., more than 4 drinks at any one sitting or more than 14 drinks/week for men; more than 2 drinks at any one sitting or more than 7 drinks/week for women) within each follow-up period (e.g., months 1-3, 4-6, 7-9, 10-12, 13-18), as determine by the TLFB. Secondary outcomes in the study will be self-reported frequency of heavy drinking days (TLFB), biological measures of alcohol use (%dCDT and GGT), urine toxicology tests to assess other drug use, VA medical records of opioid overdoses, depression, and pain. Outcome data will be analyzed using mixed effect regressions for continuous and categorical data (i.e., SAS) and various packages to examine mediation effects (i.e., MPlus). The alpha level for the primary outcome will be set at 5%.

Data quality will be monitored by random inspection of the completed forms by the research coordinator and any problems detected will be discussed with the PI. The Research prevention counselors will receive standardized training on the interventions, which are all manualized. Adherence to the manuals will be monitored using audiotapes and individual supervision provided by the clinical coordinator. If drift is observed the counselors will be re-trained.

Blind interim analyses of the data will be conducted at two points when 50 and 75% of the sample has been accrued. If the results show statistically overwhelming significant differences between groups, the study will be stopped (or one of the conditions stopped).

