**We will re-consent current subjects.**

We also note that there was no data loss to due to the VA DMU failure.

**July 2016 Amendment – An amendment to the protocol has been made to change the server back to the secure server at the VA. The reason for this is an issue with software and being able to get through the VA firewall for data entry.**

2. Provide a listing of the exact research data that will be stored, including but not limited to signed, original informed consent and HIPAA authorization forms, case report forms, etc. **Consents, HIPAA authorization, CRFs, blood and urine results, recordings from counseling phone calls. Being entered into DMU will be: dates of research visits, responses to questionnaires and interviews, as well as urine specimen and blood test results.**
3. Indicate how project's research data (original and all copies) will be stored and provide corresponding security systems. **Consents will be kept in binders in locked cabinets within the MIRECC suite at CMCVAMC. Paper Case Report Forms will be kept in a locked drawer in a locked office separate from the consents. All data will be entered into a web-based data entry system on a VA server. In addition, if a Veteran is in the PI condition and has consented to audio recording of their counseling session, we will be using digital recorders to capture the call, and then we will save the audio files of the call to the server (<https://vhaphimulh12.v04.med.va.gov/dmumain/>).**
4. Provide exact location where research data (original and all copies) will be stored and secured. **Data will be stored in the MIRECC Suite, 2nd floor of Bldg 2. Veteran contact data for follow up and tracking purposes will be kept on the research server “[name] – PI with Vets.”**
5. Explain how data is to be transported or transmitted from one location to another. **Phone numbers and participant id numbers will be transmitted to Wellpass through their website ([www.wellpass.com](http://www.wellpass.com)) which will be accessed using a secure CMCVAMC computer and network. Participant id numbers, serum samples, session dates, and blood test results will be transferred to/from MUSC via a password-protected spreadsheet on an encrypted USB device. Data stored on DMU can be entered from the location at which the data is collected. It is transmitted via internet portal.**

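### The Brief Intervention shared by both arms can be given after assignment, at the discretion of counselors who also deliver PI, and no comparison of its delivery by arm is planned

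*Combined protocol and SAP*

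**What the plan says.** **Structure of the arms.** Under O.1, the BIO group receives a BI and nothing further, while the PI group receives a BI plus tailored texts and telephone calls.

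**Content and dose of the BI.** O.1, Brief Intervention (BI), sets a common aim and a length of about 20 minutes by phone, but says that "the details on how to accomplish those goals will vary based on each Veteran's individual situation". Sending the workbook is optional. So are one or two follow-up calls about a month later.

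**Timing.** The same section says "Both groups will have received or will be scheduled to receive Brief Intervention (BI"). In the screening outcomes earlier in O.1, "a study counselor will complete the Brief Intervention only after participant has been consented to participate in the study"; that ties the BI to consent, not to randomisation. For Veterans who were not drinking at entry, O.1 says "If they report having a drink of alcohol, we will then begin which treatment arm they had been randomized to".

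**Who gives it.** R.10.5.6.4 lists among the research counselors' duties that they "provide assessment, brief interventions, telephone monitoring and counseling phone calls, and monitor text messages". There is one exception. If staff judge at baseline that a Veteran's "drinking warrants a referral to the Behavioral Health Lab (BHL) then the BHL will administer the BI".

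**Oversight.** Behavioral Health Lab (BHL) staff supervise study-delivered BIs (O.1). The clinical liaison monitors counselors' calls (R.10.5.6.4). W.1 says that "Adherence to the manuals will be monitored using audiotapes and individual supervision provided by the clinical coordinator", with retraining if drift is seen.

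**Recording.** Y.3 provides for saved recordings "if a Veteran is in the PI condition and has consented to audio recording of their counseling session". The PI Overview in O.1 also describes recording, within the account of PI. Y.1 says that calls between participants and research counselors are recorded and sets no limit by arm.

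**The concern.** The group term in the primary model is read as the effect of adding PI to a BI. That reading needs the BI to be the same, on average, in both arms. Variation by a Veteran's needs is harmless, because randomisation balances it. Variation by arm is not.

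A counselor who knows the arm has understandable reasons to adapt. The BI might be shortened for someone about to start 12 months of contact. The optional follow-up calls might go mainly to someone who will get nothing else. Techniques from the PI manual might carry over into a BIO session. A fuller BI in PI would inflate the estimated effect; a fuller BI or more follow-up calls in BIO would dilute it. The plan collects no measure of BI delivery by arm that would let a reader tell which, if either, had happened.

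**Working it through.** The point disputes no figure in the plan, so the main check sets the relevant sections side by side.

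1. **Does the BI come after assignment?** For baseline non-drinkers who later report a drink, yes: they are randomised at entry and the arm starts afterwards (O.1). The March 2018 amendment text plans 50 such Veterans of 200, and only those who report a drink before the 9-month visit get a BI at all. For baseline drinkers the order is not stated. The BI may already have been given or only be scheduled, and no section requires it before randomisation.
2. **Does the counselor know the arm?** This is an inference. The same role gives the BI, makes the PI calls and monitors the texts (R.10.5.6.4). The double-blind box in M.2.1 is not ticked, and no section withholds the assignment until the BI is done.
3. **Is there room for delivery to differ?** Yes: content, workbook and zero to two follow-up calls are discretionary (O.1).
4. **Would the planned checks show a difference by arm?** They could catch poor practice by a counselor. They do not include a BI fidelity score, a log of length, materials or follow-up calls, or a comparison between arms. The timeline in O.2.2 names manuals for PI only, and the BHL practice against which BIs are supervised itself permits the variation in step 3.
5. **Are BI calls recorded?** Y.1 implies yes in both arms. Y.3 and the PI Overview describe recording in terms of PI. None of the three names the BI call.

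**Illustration of sensitivity.** The documents give no size for a BI difference, so the gaps below are assumptions.

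Inputs from the plan: 35% against 20% risky drinking (W.4.1, March 2018 Amendment), five repeated binary outcomes (W.4.1), alpha 5% (W.1). Assumed: two-sided test, 75 per arm (half of the 150 planned to enter treatment), no loss, five visits for everyone, within-subject correlation ρ of 0.3 to 0.5.

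Design factor: (1 + 4ρ)/5, which is 0.44 at ρ = 0.3, 0.52 at 0.4 and 0.60 at 0.5.

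The plan's own total first. The pooled two-proportion formula gives about 138 per arm for 35% against 20% at 80% power. Unrounded, 2 × 137.9 × 0.44 / 0.9 = 135 and 2 × 137.9 × 0.52 / 0.9 = 159, against the stated 136 to 162. The ρ values and the 10% average loss are my assumptions, since the amendment does not state its own.

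Effective n per arm is 75/0.44 = 170 at ρ = 0.3 and 75/0.60 = 125 at ρ = 0.5. With d the difference in rates, SE₀ the pooled and SE₁ the unpooled standard error, the rejection probability is Φ((d − 1.96·SE₀)/SE₁) plus the opposite tail.

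Worked case, 35% against 30% at ρ = 0.3: SE₀ = √(2 × 0.325 × 0.675/170.5) = 0.0507; SE₁ = √((0.2275 + 0.21)/170.5) = 0.0507; (0.05 − 1.96 × 0.0507)/0.0507 = −0.98; Φ = 0.164, plus 0.002, gives 0.166.

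| Assumed BI difference | Added PI has no effect, BI difference favours PI: rejection rate | Designed effect real, BI difference lowers the BIO rate: power |
|---|---|---|
| 0 points | 5% | 0.76-0.88 |
| 3 points | 8-9% | 0.58-0.72 |
| 5 points | 13-17% | 0.45-0.57 |
| 10 points | 41-52% | 0.16-0.20 |

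Ranges run over ρ = 0.5 to 0.3.

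**The case against.** Four arguments deserve weight.

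- **The variation described is by Veteran, not by arm.** O.1 ties flexibility to the individual's situation, and flexible BHL practice is the intended comparator (H.4 makes that program the standard care arm). This stands as a defence of flexibility. It does not answer flexibility exercised by someone who may know the arm.
- **There is oversight, and it is not limited to PI.** BHL supervision, the liaison's call monitoring and the W.1 checks carry no arm restriction. A reader might infer that BIs in BIO are never checked, or that a difference would go unnoticed; the documents do not support that. What stands is narrower: none of these checks is planned as a comparison of BI delivery between arms.
- **Recording may cover everyone.** A reader of Y.3 alone might infer that the BI is recorded only in PI. Y.1 contradicts this, and Y.3 and the PI Overview do not say that the BI call is recorded even in PI. The supportable statement is that the three places conflict.
- **Any difference may be small.** In the sponsor's earlier telephone care study (H.9.a), three extra sessions moved risky drinking only from 56% to 51%, not significantly. Variation around one 20-minute call could do less. This is fair, and it is why no gap in the table should be read as an estimate.

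Masking has limits too. It cannot cover follow-up calls a month later without holding up PI, and BIs given by the BHL lie outside study staff's control.

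**Conclusion.** The point holds in a limited form. A component common to both arms has discretionary content and dose, and is given mostly by the counselor role that also delivers PI. It necessarily follows randomisation for baseline non-drinkers who later report a drink; for other Veterans its order relative to assignment is unspecified. Delivery could therefore differ by arm in either direction, and the plan has no comparison that would show it. That counselors know the arm at the time of the BI is inferred from the absence of any rule, not stated.

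The size is unknown. The illustration shows only that the primary contrast would be sensitive if a gap of several points arose. A reader might turn the 20-50% non-response in H.8.b into a 50-80% BI effect and call the BI the main active ingredient. That does not follow: the complement is an uncontrolled rate of change and cannot be ranked against 12 months of PI. Nor do the documents support assigning any share of the 15-point design difference to unequal BIs.

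The change is worth making because it closes a route to bias at little cost. The point does not show that the trial is biased.

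**What to change.** 1. **Release of assignment (O.1).** State that, for study-delivered BIs, the assignment goes to the counselor and the Veteran only after the initial BI call is logged as complete. For baseline non-drinkers randomisation stays at entry, and the assignment stays sealed until the BI that follows the first reported drink.
2. **Recording (PI Overview, Y.1, Y.3).** Reconcile the three so that consented BI calls are recorded in both arms, and bring a sample from each arm into the review already described in W.1.
3. **BI log.** For every BI, including those given by the BHL, record deliverer, date, length, materials sent and follow-up calls. Report these by arm. The log matters most for the optional follow-up calls, which a sealed assignment cannot mask.

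The cost is a short delay in disclosing the arm, a brief form per BI, and some extra recordings to review. PI itself opens with the BI (H.7), so waiting for that one call takes little from PI. Recorders and a reviewing clinician are already in place. The endpoint, the sample size and the content of either arm do not change.
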